### **5.2.2 Basiliximab (Simulect®)**

Two IV doses of basiliximab, a monoclonal antibody IL-2 receptor blocker, will be given with the first and second (if necessary) transplants. The first dose will be 20 mg and will be given within two hours prior to islet transplant on the day of islet transplantation. The second 20 mg dose will be given on Day 4 after the transplant.

If a third transplant is deemed necessary and performed between 30 and 70 days after the second transplant, no additional doses of basiliximab will be given.

If a third islet transplant is deemed necessary and performed more than 70 days after the second transplant (see Section 7.6 for indications for subsequent transplants), both doses of basiliximab will be repeated.

### **5.2.3 Tacrolimus (Prograf®)**

Tacrolimus may be used only as a supplement to MMF in those cases where the trough level is below the therapeutic range as outlined in section 5.2.1. Tacrolimus will be administered orally twice a day to maintain trough levels of 3-5 ng/mL. Generic equivalents of Prograf® will not be permitted.

## **5.3 Concomitant Medications**

### **5.3.1 Antibacterial, Antifungal, and Antiviral Prophylaxis**

Broad spectrum antimicrobial prophylaxis should be administered preoperatively according to site-specific standards, or as the Transplant Infectious Disease consultant recommends.

#### **5.3.1.1 TRIMETHOPRIM/SULFAMETHOXAZOLE (SEPTRA SS®/BACTRIM®)**

Trimethoprim/sulfamethoxazole will be administered at a dose of 80 mg/400 mg PO QD starting on Day +1 for 6 months after each transplant. In the event that a subject is unable to take trimethoprim/sulfamethoxazole, he/she will be treated on a case-by-case basis as is medically indicated. Dapsone is contraindicated in the setting of this trial due to its known

interaction with the HbA1c assay, which would have an effect on interpretation of endpoint outcomes for the trial.

#### 5.3.1.2 VALGANCICLOVIR (VALCYTE®)

Valganciclovir will be administered starting on Day -2, for initial transplants, Day -1 for subsequent transplants, at a dose of 450 mg PO QD, increasing to 900 mg QD by Day 12 and continuing for 14 weeks post-transplant. If the CMV status of the donor and recipient are both negative, then valganciclovir administration can be adjusted or eliminated.

### 5.3.2 Anticoagulation Prophylaxis / Hematological Agents

#### 5.3.2.1 HEPARIN

Heparin will be administered at a dose of 70 U/kg body weight of recipient, divided equally among the islet bags, given with the islet infusion, followed by 3U/kg/hr IV for the next 4 hrs. From the 5th through the 48th hr post-transplant heparin, will be titrated to achieve and maintain partial thromboplastin time (PTT) between 50-60 seconds. If a site does not use PTT to titrate heparin, a comparable site-specific method and value should be used.

#### 5.3.2.2 ENOXAPARIN (LOVENOX®)

Enoxaparin will be administered at a dose of 30 mg SC BID through day 7 post -islet transplant, with the first dose given 48 hours after the transplant procedure (when heparin is discontinued). The dose can be modified or extended at the discretion of the investigator.

#### 5.3.2.3 ASPIRIN

Enteric coated aspirin will be administered at a dose of 81 mg PO qPM starting 24 hrs post-transplant and continued as medically indicated.

#### 5.3.2.4 PENTOXIFYLLINE

Pentoxifylline will be administered at a dose of 400 mg slow release TID beginning 2 days prior to transplant (Day -2) and continuing for 7 days post-transplant (Day 7).

### 5.3.3 Updated Vaccinations

Subjects will remain up to date on CDC-recommended adult vaccinations; please refer to the MOP for guidance. Live vaccines should be avoided while taking belatacept.

### **5.3.4 Insulin Therapy**

Glucose levels will be targeted to 80-120 mg/dL. Insulin (e.g., Regular, Lispro, NPH, Glargine) will be administered as needed to maintain glucose levels in the target range. The subject will test BG five times per day (AM fasting, before lunch, 2 hours after lunch, before supper, and at bedtime). The subject's daily BG levels will be reviewed by a study nurse and/or one of the investigators three times per week during the first two weeks after discharge, and then weekly during the next month. Exogenous insulin will be withdrawn or adjusted as needed. Patients able to maintain fasting BG levels below 140 mg/dL and 2-hour post-prandial levels below 180 mg/dL after insulin discontinuation will be considered insulin independent.

### **5.3.5 Other Standard Therapies**

Anti-hypertensive, anti-hyperlipidemia and other approved therapies for pre-existing and new medical conditions will be provided per standard of care. Pre- and post -islet transplant procedure drug regimens (e.g., pre-transplant sedation and anesthetic) will be given per standard of care.

## **5.4 Rescue Medications**

Rescue therapy will not be initiated in this protocol to treat suspected rejection. Immunologic surveillance methods that would allow diagnosis of islet allograft rejection early enough for timely intervention have yet to be identified and validated.

## **5.5 Prohibited Medications**

Prohibited medications for this protocol, except as specifically indicated in this protocol include:

- steroid medication (save topicals and prednisone at a dose of  $\leq 5$  mg daily, or an equivalent dose of hydrocortisone, for physiological replacement only)
- any medications in the macrolide antibiotic class other than Zithromax
- other investigational products
- other immunosuppressive therapies
- immunomodulatory agents
- other anti-diabetic agents
- Dapsone
- azathioprine
- cholestyramine or other agents that may interfere with enterohepatic recirculation
- live vaccines
- sevelamer or other calcium free phosphate binders

## 5.6 Assessment of Compliance with Study Treatment

Assessment of subject compliance will be determined by the completion of scheduled study visits and required documentation that the specific subject is responsible for (e.g., Blood Glucose Logs, AE and Insulin Use recording) as well as their willingness to comply with the recommendations of the study investigators. Any aberration of trough levels of immunosuppressive agents that could indicate nonadherence, lack of compliance that poses a significant clinical risk and / or derangement of protocol data collection will be documented. Please refer to Section 5.7.2 for a description of possible indications for premature discontinuation of study treatment.

## 5.7 Modification or Discontinuation of Study Treatment

### 5.7.1 Modification of Consensus Immunosuppression

#### 5.7.1.1 INTOLERANCE OF PROTOCOL MEDICATIONS

In the event that protocol-regulated concomitant medications are not tolerated, the subject will continue taking the immunosuppressive therapy in order to protect the islet graft. In the event that the immunosuppression regimen is not tolerated, the Site principal investigator (PI) may elect to prescribe an alternative immunosuppression regimen. The intent would be for the alternative regimen to be temporary in nature where possible. Any non-protocol directed study treatment modification that the site PI determines is necessary should be reported as a protocol deviation.

#### 5.7.1.2 GRAFT FAILURE

Subjects who experience graft failure will be maintained on their current immunosuppressive regimen as long as a subsequent transplant is possible. If/when it is determined that a subject will not receive a subsequent transplant, then immunosuppression will be stopped and the subject will move to the reduced follow-up schedule (see section 5.7.2).

#### 5.7.1.3 NEUTROPENIA

Neutropenia is an expected consequence of the administration of several medications in this protocol. Subject safety is of utmost importance. Clinical treatment decisions take precedence over recommended guidelines.

**If a subject's absolute neutrophil count is less than 1000 cells/ $\mu$ L and the subject is afebrile, then the following will be done:**

- Reduce the prophylactic use of valganciclovir from 900 mg per day to 450 mg per day or hold valganciclovir.
- Reduce trimethoprim/sulfamethoxazole to 80/400 mg on Monday, Wednesday, and Friday or hold trimethoprim/sulfamethoxazole.
- Consider reducing the dose of mycophenolate mofetil.

- Consider administration of G-CSF.
- Monitor temperature BID.
- Follow-up within 48-72 hours to obtain: repeat complete blood count (CBC) with differential, patient symptoms, and measured temperatures.

**If a subject's absolute neutrophil count is less than 1000 cells/ $\mu$ L and the subject is febrile, then the following will be done:**

- Obtain Infectious Disease Consult.
- Hold valganciclovir and trimethoprim/sulfamethoxazole.
- Consider reducing the dose of mycophenolate mofetil.
- Obtain CMV antigenemia or PCR for CMV.
- Administer G-CSF.
- Monitor temperature BID.
- Follow-up within 48-72 hours to obtain: repeat CBC with differential, subject symptoms, and measured temperatures.

**If a subject's absolute neutrophil count is measured as less than 500 cells/ $\mu$ L and the subject is afebrile, then the following will be done:**

- Hold administration of trimethoprim/sulfamethoxazole and/or valganciclovir.
- Consider holding dose of mycophenolate mofetil.
- Obtain CMV antigenemia or PCR for CMV.
- Consider fluoroquinolones in afebrile subjects.
- Consider clotrimazole.
- Administer G-CSF.
- Monitor temperature BID.
- Follow up within 24 hours to obtain repeat CBC, subject symptoms, and measured temperatures.

**If a subject's absolute neutrophil count is measured as less than 500 cells/ $\mu$ L and the subject is febrile, then the following will be done:**

- The patient will be hospitalized under neutropenic precautions and Infectious Disease/Hematology consult will be obtained.
- Hold administration of trimethoprim/sulfamethoxazole and/or valganciclovir.
- Consider holding dose of mycophenolate mofetil.
- Obtain CMV antigenemia or PCR for CMV.
- Administer G-CSF.
- Follow up within 24 hours with admitting physician.

#### 5.7.1.4 THROMBOCYTOPENIA

If the subject is found to have a platelet count (PLT) of  $<50 \times 10^9/L$ , mycophenolate mofetil will be withheld for 24 hours, then resumed at a 50% reduced dose. If PLT fails to return to  $>50 \times 10^9/L$  within one week, mycophenolate mofetil is to be withheld until PLT  $> 50 \times 10^9/L$ , after which MMF is resumed at 50% of the dose that preceded the drop in PLT to  $< 50 \times 10^9/L$ .

#### 5.7.2 Premature Discontinuation of Study Treatment (Transition to “Off-Protocol” Treatment)

Study treatment may be prematurely discontinued for any subject for any of the following reasons:

1. The subject is unwilling or unable to comply with the protocol.
2. The investigator believes that the study treatment is no longer in the best interest of the subject.
3. Graft Failure (see Study Definitions).
4. Any clinical AE, laboratory abnormality, or intercurrent illness which, in the opinion of the investigator, indicates that continued treatment with study therapy is not in the best interest of the subject. The agent(s) to which the event is attributed will be discontinued.
5. The subject becomes pregnant
6. Missing 2 consecutive belatacept infusions
7. The development of belatacept is terminated by the manufacturer (BMS)
8. The subject is imprisoned or compulsorily detained for the treatment of either a psychiatric or physical illness (e.g., infectious disease).

Subjects who prematurely discontinue study treatment will remain in the study until normal termination, for the purpose of monitoring safety and efficacy parameters and will enter the reduced follow-up scheduled outlined in Appendix 5. Data from these subjects will be used in the intent-to-treat analysis. These subjects are permitted to simultaneously enroll in a CIT or site-specific graft failure follow-up protocol, if available.

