## Study Definitions

Full Graft Function	Islet transplant recipients will be considered to have full islet graft function if they are insulin independent.
Graft Failure	Islet allograft failure will be defined as absence of insulin production by transplanted islets, as evidenced by c-peptide < 0.3 ng/mL. This will be determined by (1) c-peptide < 0.3 ng/mL on random testing, followed by (2) c-peptide < 0.3 ng/mL at baseline, and at 60 and 90 minutes after MMTT. C-peptide levels obtained in the course of the MMTT will be run at the core lab in Seattle, WA; allow 72 hours for results. Participants with graft failure do not need to complete the day 75 metabolic assessments.
Insulin Independent	
Subjects will be considered insulin independent if they are able to titrate off insulin therapy for at least 1 week and all of the following criteria are met:
 

• One HbA1c level, one fasting serum glucose level, and a Mixed Meal Tolerance Test are documented within the visit window (e.g. 70-80 days at Day 75) and 7 consecutive days of blood sugar and insulin readings are documented within +/- 7 days of the visit window (e.g. 63 - 87 days at Day 75);

• HbA1c < 7.0% or ≥ 2.5% decrease from baseline;

• Fasting capillary glucose level should not exceed 140 mg/dL (7.8 mmol/L) more than three times in 7 consecutive days (fasting is defined as 1st blood sugar reading of the day not noted as post-prandial or bedtime);

• Post-prandial serum glucose ≤ 180 mg/dL (10.0 mmol/L) at 90 minutes during the MMTT;

• Fasting serum glucose level ≤ 126 mg/dL (7.0 mmol/L); if the fasting serum glucose level is > 126 mg/dL (7.0 mmol/L), it must be confirmed in an additional one out of two measurements;

• At least one MMTT fasting or stimulated c-peptide ≥ 0.5 ng/mL.

Insulin Dependent	Islet transplant recipients who do not meet the criteria for insulin independence will be considered insulin dependent.
Intensive Diabetes Management	Self monitoring of glucose values no less than a mean of three times each day averaged over each week and by the administration of three or more insulin injections each day or insulin pump therapy.
Partial Graft Function	Islet transplant recipients who do not meet criteria for insulin independence, but have either a basal or stimulated c-peptide level ≥ 0.3 ng/mL (0.1 nmol/L).

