## 4.1 Study Endpoints

### 4.1.1 Primary Endpoint

The primary endpoint for this study is the proportion of **insulin-independent** subjects at day 75 ( $\pm 5$  days) following the first islet transplant.

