### **7.5 Follow-up Visits**

Subject will undergo a 24-month follow-up period following their final islet transplant. Please refer to the Schedule of Events (Appendices 1, 2, 3, and 4), for the clinical time points of specific follow-up study procedures.

All subjects will follow the Year One Schedule of Events (Appendix 1) in its entirety. Subjects who receive a subsequent islet transplant will continue onto Appendix 2, Continuation of Appendix 1 Schedule of Events (Subjects with Subsequent CIT Transplants) until they reach their one year visit after the final islet transplant. In addition to following Appendix 2, all

subjects who receive a subsequent transplant should complete the assessments listed on the Subsequent Transplant Schedule of Events (Appendix 3), which provides immediate post-transplant and endpoint day assessments. After the one year post-final transplant visit, subjects will move to Appendix 4, Schedule of Events for 1-Year Additional Follow-up.

Subjects are ineligible for subsequent islet transplantation in the CIT04 protocol as of 8 months following their initial transplant (between visits 16 and 17). After visit 21 (365 days following transplant) has been completed, study subjects may obtain a subsequent islet transplant outside of CIT04. Subjects will be followed for adverse events only until until 24 months after their final CIT islet transplant.

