### **10.2 Study Endpoint Assessment**

#### **10.2.1 Primary Endpoint**

The primary objective of the analysis is to estimate the rate of insulin independence at 75 days after the first islet transplant. The primary endpoint is insulin independence (yes/no) at day 75 after islet transplant as defined in section 4.1.1. The primary analysis will compute an exact binomial estimate and a 95% confidence interval for the true rate. If the results of this trial show at least 10% insulin independence in the context of evaluation all of the secondary endpoints, the investigators will consider this grounds for further investigation.

The primary analysis will consist of the intent-to-treat population. An exception will be if a death occurs or if the subject withdraws consent to be followed, in these cases the endpoint will be classified as failure to achieve insulin independence. Should the endpoint not be evaluated for a particular individual for other reasons, a failure will be imputed unless an evaluation is done at a time longer than 75 days after transplant and before an additional islet transplant, in which case that later value will be imputed. All imputations will be reported with the primary analysis.

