#### **REDUCED FOLLOW-UP SCHEDULE**

Complete the following assessments at the intervals (+/- 7 days) indicated below relative to the day the subject discontinued study treatment. Continue conducting these assessments at the defined intervals until the subject reaches two years post **last** transplant.

- Assess SAEs and hypoglycemic events: q1 month. If subject does not come to the study site for the visit, attempt to obtain information via a phone contact.
- Alloantibody (central lab): q 1 month for the first 3 months and q 3 months thereafter.
- Immunogenicity Samples: for subjects who discontinue belatacept, collect samples at 4 weeks and 8 weeks post last dose

Complete the following assessments at 1 and 2 years (+/- 14 days) post **initial** transplant:

- Assess SAEs and hypoglycemic events
- Alloantibody (central lab)
- HbA1c (central lab)
- 90 minute c-peptide post MMTT (central lab)
- Serum creatinine (central lab)
- QOL questionnaire (via mail or in-person)

Complete the following assessments at 1 and 2 years (+/- 7 days) post **last** transplant:

- Assess SAEs and hypoglycemic events
- QOL questionnaire (via mail or in-person)

*Appendix 6: Study Contacts*

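### For subjects who stop study treatment before Day 75 without graft failure, 5.7.2 and Appendix 5 conflict with 7.5 on whether the primary endpoint is measured; if Appendix 5 is followed, they are scored as failures unassessed.

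*Protocol*

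**What the plan says.** All places are in the protocol.

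- **Primary endpoint (4.1.1).** The proportion of insulin-independent "subjects at day 75 ( $\pm 5$ days) following the first islet transplant".
- **What classification needs (Study Definitions, Insulin Independent).** "One HbA1c level, one fasting serum glucose level, and a Mixed Meal Tolerance Test are documented within the visit window", together with seven consecutive days of glucose and insulin readings close to that window. The criteria include limits on fasting serum glucose and on the 90-minute meal-test glucose. The default is stated separately: "Islet transplant recipients who do not meet the criteria for insulin independence will be considered insulin dependent".
- **Early stoppers (5.7.2).** They remain in the study but "will enter the reduced follow-up scheduled outlined in Appendix 5. Data from these subjects will be used in the intent-to-treat analysis".
- **Appendix 5.** Its interval items are serious adverse events, hypoglycemic events, alloantibody and immunogenicity samples. Metabolic tests first appear under the instruction "Complete the following assessments at 1 and 2 years (+/- 14 days) post" the initial transplant, and are HbA1c, a 90-minute C-peptide and serum creatinine.
- **Follow-up in general (7.5).** "All subjects will follow the Year One Schedule of Events (Appendix 1) in its entirety". The Day 75 column of Appendix 1 contains HbA1c, fasting glucose, the meal test and the blood sugar record.
- **Missing primary endpoint (10.2.1).** For an endpoint not evaluated for reasons other than death or withdrawn consent, "a failure will be imputed unless an evaluation is done at a time longer than 75 days after transplant" and before any further transplant. All imputations are to be reported.
- **Graft failure (Appendix 1, footnote 19).** Tests done when the graft failed supply the Day 75 result.

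**The concern.** A subject can stop study treatment before Day 75 with a graft that still works. Section 5.7.2 lists adverse events, pregnancy, investigator decision and two consecutive missed belatacept infusions among the reasons. Sections 5.1.2.2 and 7.4 schedule infusions on Days 0, 4, 14, 28, 56 and 84, so the missed-infusion reason can arise by Day 14, 28 or 56. Missing Days 56 and 84 triggers it only after the endpoint visit.

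A site that follows 5.7.2 and Appendix 5 would drop the Day 75 metabolic visit for that subject. A site that follows 7.5 would keep it. Under the Appendix 5 reading, the schedule itself creates a missing primary outcome in a subject who may be present and willing to be tested. The primary rate would then combine loss of graft function with stopping the regimen, and the data could not separate the two. With 10 subjects, and a rate of at least 10% named as grounds for further work, one subject can matter.

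**Working it through.** **1. Can an Appendix 5 subject ever be classified as insulin independent?**

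| Needed for classification | Appendix 1, Day 75 | Appendix 5 |
|---|---|---|
| HbA1c | yes | 1 and 2 years after initial transplant only |
| Fasting serum glucose | yes | not listed |
| Meal test, 90-minute glucose | yes | not listed |
| Meal test, C-peptide | yes | 90 minutes, 1 and 2 years only |
| 7-day glucose and insulin record | yes | not listed |

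The answer is no, at Day 75 or at any later Appendix 5 visit. The provision in 10.2.1 for a later evaluation therefore cannot help unless tests are done outside the schedule. The result is an imputed failure.

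**2. The plan's own figures.** Table 5 (section 10.4) gives exact 95% intervals for n = 10. With x successes, the lower limit is the 0.025 quantile of Beta(x, n − x + 1) and the upper limit is the 0.975 quantile of Beta(x + 1, n − x). The limits are 0 at x = 0 and 1 at x = n. All 11 rows reproduce to four decimals, so no stated figure is wrong.

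**3. Effect on the estimate.** Let d be the number of subjects who stop before Day 75 without graft failure and go unmeasured. The reported rate is x/10. The rate had they been measured lies between x/10 and (x + d)/10, so the shortfall is between 0 and d/10.

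| Reported | d | Highest value had all been measured |
|---|---|---|
| 0/10 (0 to 30.85%) | 1 | 1/10 (0.25 to 44.50%) |
| 3/10 (6.67 to 65.25%) | 1 | 4/10 (12.16 to 73.76%) |
| 3/10 (6.67 to 65.25%) | 2 | 5/10 (18.71 to 81.29%) |

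Put the other way, a true 5/10 (18.71 to 81.29%) would be reported as 4/10 (12.16 to 73.76%) if one of the five successes stopped early and went untested.

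**4. Effect on the 10% mark.** Section 10.2.1 names at least 10%, which is 1 of 10. With d subjects forced to failure and the rest independent with success probability p, the chance of reaching it is 1 − (1 − p)^(10 − d). For example, at p = 0.10 with d = 1 it is 1 − 0.9^9 = 61.3%.

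| True rate p | d = 0 | d = 1 | d = 2 | d = 3 |
|---|---|---|---|---|
| 10% | 65.1% | 61.3% | 57.0% | 52.2% |
| 30% | 97.2% | 96.0% | 94.2% | 91.8% |

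The values of d are assumptions, because the protocol gives no rate of stopping before Day 75. Its background section reports that 17.6% and 21.1% of belatacept subjects in the phase 2 kidney study discontinued for adverse events. That is a different population with mean exposure of 300 and 308 days, so it shows only that discontinuation is not negligible.

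**The case against.** **A reader might infer a breach of intention to treat.** The documents do not support that. Section 10.1 accounts for every subject who receives belatacept or islets. Section 10.2.1 prespecifies the failure rule and reports every imputation, and the subject stays in the denominator. Counting missing as failure is conservative in a single-arm pilot. Because the objective in 2.1 concerns the immunosuppressive regimen, treating an early stop as non-success is defensible. What remains is that an obtainable outcome may not be collected, so the two readings of the rate cannot be shown side by side.

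**A reader might infer that every early stopper is affected.** That is too broad. Graft failure is covered by footnote 19. A C-peptide below 0.3 ng/mL cannot meet the 0.5 ng/mL criterion, so that failure is observed. Subjects who are unwilling to comply may not be testable under any schedule, and some listed reasons also appear in 6.1 as grounds for leaving the study.

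**A reader might link this to alternative regimens under 5.7.1.1.** That section deals with intolerance and does not itself move anyone to Appendix 5; the transfer comes from 5.7.2.

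**A reader might say that 5.7.2 promises efficacy data and Appendix 5 delivers none.** The wording is "for the purpose of monitoring safety and efficacy parameters and will enter the reduced follow-up scheduled outlined in Appendix 5", and Appendix 5 does collect hypoglycemic events and the one-year HbA1c, the components of the key secondary endpoint. The text does not specifically promise the Day 75 result.

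**Section 7.5 may already preserve the visit.** It can be read that way, so omission is not certain. It does not settle the matter, because 5.7.2 and Appendix 5 give the more specific instruction for these subjects.

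**Conclusion.** The point holds in a limited form. For a subject who stops study treatment before Day 75 for a reason other than graft failure and stays in the study, the protocol gives two incompatible follow-up instructions. Under one of them the primary endpoint is imputed as failure without assessment.

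The size is up to 10 percentage points per subject, and zero where the subject would not have been insulin independent. A flat loss of 10 points for each early stopper is not supported. The consequence is greatest at the bottom of the scale, where one untested success would turn 1/10 into 0/10. Even there, 10.2.1 weighs the 10% mark together with all the secondary endpoints, so it is not a mechanical rule. At a true rate of 30%, one forced failure changes the chance of reaching the mark only from 97.2% to 96.0%.

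The conclusion rests on Appendix 5 being followed as written and on at least one such subject occurring, for which the documents give no expected frequency. The change is still worth making, because it removes schedule-made missing data from the primary endpoint of a 10-subject trial.

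**What to change.** Reconcile 5.7.2, 7.5, 10.2.1 and Appendix 5 as follows:

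- Subjects without graft failure who stop study treatment before Day 75 and consent to continued assessment keep the existing Day 75 HbA1c, fasting serum glucose, meal test (with 90-minute glucose and C-peptide) and seven-day glucose and insulin record.
- The intention-to-treat primary analysis uses their measured result.
- Failure imputation stays for those who decline or cannot be assessed, and footnote 19 stays for graft failure.
- 7.5 states which subjects leave Appendix 1, when they leave, and which of its visits they retain.
- The report gives the number off study treatment at Day 75 and shows alongside the primary result the rate obtained when those subjects are counted as failures.

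The cost is a short amendment and one already designed visit retained for a few subjects at most. The sample size, the interval method and Table 5 do not change, and the fix concerns assessments only, not treatment.
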